Results: Our results showed that Silodosin turned out to be better in expulsing stone as well as in producing lesser side effects and hence better safety profile than Tamsulosin. Silodosin showed greater stone expulsion rate with about 55 patients expulsing stone in less than 14 days in comparison to just about 5 patients on Tamsulosin. Similarly, patients on Silodosin, showed lesser side effects as compared to Tamsulosin. Nine patients on tamsulosin (60.0%) and six patients on silodosin (40.0%) developed orthostatic hypotension. Only a very tiny percentage of patients reported abnormal ejaculation; two individuals on tamsulosin (66.7%) and one patient on silodosin (33.3%). Another side effect that was identified involved headaches, seen by four patients on silodosin (44.4%) and five patients on tamsulosin (55.6%).

INTRODUCTION

Stone disease is one of the most frequent presentations in the field of urology. A large number of these patients arrive with ureteric stones(1). Globally, occurrence of stone formation is 10-12% for men and 6-8% for women. Its prevalence in Pakistan is approximately 16%. The disease's burden has increased in all age categories and both genders over the past 20 years(2). The incidence of urolithiasis in different age groups is 12.2% in the persons 20-29 year old, 29.6% in those who are 30-39-year-old, and 31.5% in 40–49-year-old patients(3).

Medical management ae well as surgical removal are various options available for treating ureteric stones as per American Urology Association (AUA) and European Association of Urology (EAU) guidelines. However, due to risks of surgical approaches there is always an attempt for treatment by using medical expulsive treatment (MET) for ureteric stones first keeping in view different parameters. According to European Association of Urology Guidelines (EAU), the ureteric stones less than 10 mm can be treated with MET(4). Medical expulsive therapy (MET) is a well-established treatment option for distal ureteric stones, despite a sharp increase in minimally invasive techniques(5). Stones smaller than 5 mm have passage rates ranging from 71% to 98%, while stones with size more than 5 mm had expulsion rates ranging from 25% to 53%(6).

Many factors affect stone removal and must be considered while selecting MET for stones like ureteric spasm, location, size, and number of stones and duration for which it is present and also the ureteric architecture etc(7).

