Data will be entered and analyzed on SPSS version 22. Percentages and frequencies will be calculated for the demographic variables of the patients. The comparison of the two groups will be made by using T- test. P-value of less than 0.05 will be considered significant and the power used will be 0.80.

RESULTS

Frequency and percentage of demographic data

Variables		Frequency	Percentage	
Gender	Male	105	58.7	
	Female	74	41.3	
Income	Less than	108	60.3	
status	50000			
	50000 -150000	69	38.5	
	Greater than	2	1.1	
	150000			
	Normal	166	92.7	
BMI	Obese	13	7.3	
	None	136	76.0	
Comorbidity	HTN	33	18.4	
	Diabetes	10	5.6	

This information sheds light on the sample population's health and demographic distribution, showing a preponderance of people with normal BMIs and lower income levels, as well as a significant percentage of people without comorbid diseases.

In our study there are total 179 patients out of which 74 are females (41.3%) and 105 males (58.7%).

The income, 108 people, or 60.3% of the total, make less than 50,000Rs in month. Just 2 members, or 1.1 percent, make more than 150,000 monthly, while 69 participants (38.5%) have monthly salaries between 50,000 and 150,000.

13 persons (7.3%) are classed as obese, while 166 people (92.7%) have a normal BMI. These numbers represent a sizable fraction of the sample. In terms of comorbidities, 136 individuals (76.0%) state they have no comorbid conditions. Of the people with comorbidities, 10 (5.6%) had diabetes, and 33 (18.4%) had hypertension (HTN).

[figure not shown]

Figure 1: Pie chart of patients using Silodosin and Tamsulosin (Medicine Advised)

Use of medicine (Figure 1)

Tamsulosin and Silodosin, the two drugs prescribed to a group of patients, are distributed as shown in the pie chart. Of the patients, 43% were advised to take Tamsulosin, which is shown as the blue section on the chart. And (57%) of the patients were advised to take silodosin, as shown by the red segment.

Table2: Patient demographic characteristics and study variables are

Varibales	Tamsulosin	Silodosin	p-value	
Body Mass index	Normal	72(43.4%)	94(56.6%)	0.730
	obese	5 (38.5%)	08(61.5%)	
Laterality	Right	65(55.6%)	52(44.4%)	0.001
	Left	12(19.4%)	50(80.6%)	
Symp To CT	Less than 1 week	67(64.4%)	37(35.6%)	
	More than 1 week	10(15.2%)	56(84.8%)	0.001
	More than 2 week	0 (0.0%)	09(100%)	
Posl n Ureler	Proximal	28(51.9%)	26(48.1%)	

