This bar chart presents a comparative examination of the rates of stone expulsion for patients who were suggested to take Tamsulosin or Silodosin during three distinct time periods—less than 14 days, 14–21 days, and 21–28 days.

The results are color-coded, with red bars denoting silodosin and blue bars denoting tamsulosin.

Silodosin shows a markedly greater efficacy in stone expulsion, with about 55 patients expulsing stone in less than 14 days in comparison to just about 5 patients on Tamsulosin.

This suggests that Silodosin is far more successful at facilitating stone removal in less time than Tamsulosin.

While in 14–21days duration, Silodosin continues to work better than Tamsulosin in removing stones. About 20 patients on Tamsulosin were able to successfully remove stone, compared to about 30 people on Silodosin. This implies that while tamsulosin is also beneficial, silodosin retains greater efficacy.

In the span of 21–28 days, 57 patients on Tamsulosin while 13 on Silodosin were able to eliminate stones. In general, Silodosin is quite successful for rapid stone ejection during the first two weeks. Using the intended period for stone

ejection to guide medicine selection, this time-dependent efficacy analysis offers clinicians important information.

[figure not shown]

Figure 3 Survival function

This statistical method is commonly used to estimate the time until an event occurs and to compare the survival curves of different groups. In this case, Kaplan–Meier analysis was performed to assess the duration that patients required to expel kidney stones while receiving either silodosin or tamsulosin treatment. The rate of the expulsion of stone and the time for it, for both groups, was evaluated using this method, as can be seen in Figure 2.

The log-rank test was applied to compare the rate and time for stone expulsion between the two groups. It is a hypothesis test for comparing the survival distributions of two samples. It was used in this study to see if patients treated with silodosin and those treated with tamsulosin had significantly different times for stones to be expelled. With a p-value of 0.05, the log-rank test findings showed that there was statistically significant difference between the two groups. This indicates that both groups' times to stone expulsion were statistically comparable.

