The data showed that patients treated with silodosin demonstrated a higher rate of stone expulsion and faster stone expulsion compared to those treated with Tamsulosin. Though the difference did not achieve statistical significance in this trial, it shows that silodosin may be more beneficial in aiding kidney stone removal. The evaluation of rate and time of stone expulsion for both groups was conducted using Kaplan–Meier analysis, as depicted in Figure 2. This statistical method is commonly used to estimate the time until an event occurs and to compare the survival curves of different groups. In this context, the Kaplan–Meier analysis was utilized to assess the duration it took for patients to expel kidney stones while being treated with either silodosin or tamsulosin.

DISCUSSION

After prostate pathology and urinary tract infections, renal stones are the third most frequent urinary tract disorder. Ureteral stones account for 14% of stones in the urinary system, most of which are in the distal ureter. Five to ten percent of people have urolithiasis. Their rising incidence is a serious cause for concern(35).

Stones can be treated medically or surgically according to European and American urology associations. The medical management (MET) has its own advantages and is preferred over surgical approach as it is has less risks involved than the surgical procedures. For (MET) medical expulsive therapy we need to keep in view various parameters including the stone's size, position, and ureteric characteristics. The medical care of ureteral calculi has significantly improved since the market saw the release of efficient medicinal therapeutic agents. The results of multiple investigations suggest that alpha blockers aid in the transit of ureteral stones. These have shown that this strategy may speed up and ease the ureteral stones' natural passage. α -AR blockers have been suggested by recent worldwide standard guidelines as a treatment for ureteral stones in adults and adolescents.

In 1970, it was initially reported on how adrenergic receptors function in the human ureter. Alph adrenergic receptor agonists preserve ureteral peristalsis, which may aid in a spontaneous stone passage, while also preventing the uncoordinated muscular activity associated with renal colic. Instead of totally stopping the action of the ureteric smooth muscle, alpha blockers primarily cause relaxation of the human ureter's distal portion.

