Similar results were seen in another study showing that, individuals receiving just tamsulosin treatment needed a greater average analgesic dosage of 391.43 \pm 165.60 mg with a p-value of 0.005, which denotes substantial significance, the necessary(50).

Similarly, a study showed statistically significant difference in the amount of analgesics needed by patients treated with Silodosin compared to those treated with tamsulosin only. The robustness of the conclusion was highlighted by the fact that the group receiving Silodosin treatment required considerably fewer analgesics than the groups receiving Tamsulosin, with a p-value of < 0.001(51).

Conclusion

An effective treatment for ureteral stones is medical expulsive therapy. According to our findings, silodosin has a safer profile and is more successful than tamsulosin at ejecting ureteric stones.

Silodosin had an increased rate of stone expulsion and took less time in stone expulsion compared to those treated with Tamsulosin.

In addition, patients treated with silodosin reported fewer side effects, such as a retrograde ejaculation, orthostatic hypotension and headaches as compared to those taking Tamsulosin.

In addition, those who received Silodosin needed less analgesic medication than those who received Tamsulosin.

•

REFERENCES

- Ahmed AFAM, Al-Sayed AYS. Tamsulosin versus Alfuzosin in the Treatment of Patients with Distal Ureteral Stones: Prospective, Randomized, Comparative Study. Korean J Urol. 2010 Mar;51(3):193–7.
- 5. Pietropaolo A, Proietti S, Geraghty R, Skolarikos A, Papatsoris A, Liatsikos E, et al. Trends of 'urolithiasis: interventions, simulation, and

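### One log-rank result (printed p of 0.05) is called significant, comparable and not significant, and read as a computed value it does not plausibly fit the report's own counts

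*Combined protocol and SAP*

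**What the plan says.** The Results text under Figure 3 (Survival function) describes a Kaplan–Meier analysis and a log-rank test of time to stone expulsion. It interprets that one test three times:

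- "With a p-value of 0.05, the log-rank test findings showed that there was statistically significant difference between the two groups".
- The next sentence says that both groups' "times to stone expulsion were statistically comparable".
- The following paragraph, after stating that expulsion was more frequent and faster on silodosin, adds: "Though the difference did not achieve statistical significance in this trial".

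The decision rule is in the Data Analysis Procedure section: "P-value of less than 0.05 will be considered significant". The only comparative test named there is a different one: "The comparison of the two groups will be made by using T- test".

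Other sections make their own statements about speed:

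- Results, Figure 2 text: "This suggests that Silodosin is far more successful at facilitating stone removal in less time than Tamsulosin".
- Abstract, Results: "Silodosin showed greater stone expulsion rate with about 55 patients expulsing stone in less than 14 days".
- Conclusion: "Silodosin had an increased rate of stone expulsion and took less time in stone expulsion compared to those treated with Tamsulosin".

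The counts behind these statements are in the Time for removal rows of the patient-characteristics table.

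**The concern.** A reader can quote this report for a significant difference in time to expulsion, for no difference, or for a difference that missed significance, all from the same test. The log-rank test is the only time-to-event test reported. The Conclusion repeats the statement of faster expulsion but drops the caveat on significance that accompanies it under Figure 3.

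Time to expulsion is not the outcome in the Operational Definitions, where stone clearance is judged on X-ray at 4 weeks. The Abstract and Conclusion still present speed as a main result, so its test must be reported in a way that can be read only one way.

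A second question is whether 0.05 can be the computed p at all, given how far apart the tabulated times are.

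**Working it through.** **1. The three statements against the decision rule.** This step needs no assumption.

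| What 0.05 is | Called significant | Called comparable | Called not significant |
|---|---|---|---|
| Computed p, exactly 0.05 | Wrong: 0.05 is not below 0.05 | Unsupported: a p at the threshold does not show similarity | Follows from the rule |
| Threshold, or misprint of p<0.05 | Follows from the rule | Wrong | Wrong |

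On either reading at least one current sentence has to go.

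**2. Inputs for the numerical check** (Time for removal rows)

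| Interval | Tamsulosin | Silodosin | Total |
|---|---|---|---|
| Under 14 days | 6 | 52 | 58 |
| 14–21 days | 14 | 37 | 51 |
| 22–28 days | 57 | 13 | 70 |
| Total | 77 | 102 | 179 |

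The total matches the 179 patients in the Results. The Figure 2 text describes the last row as expulsions. Cumulative removal before day 14 is 6/77 = 7.8% against 52/102 = 51.0%. By day 21 it is 20/77 = 26.0% against 89/102 = 87.3%.

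**3. Grouped log-rank test, tamsulosin arm.** In each interval, with n_T and n_S at risk, N = n_T + n_S, and d removals:

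E = d·n_T/N and V = d·(n_T/N)·(n_S/N)·(N−d)/(N−1)

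- Under 14 days: E = 58×77/179 = 24.95; V = 58×(77×102/179²)×(121/178) = 9.66.
- 14–21 days (71 and 50 at risk): E = 51×71/121 = 29.93; V = 51×(71×50/121²)×(70/120) = 7.21.
- 22–28 days (57 and 13 at risk, all 70 removed): E = 57; V = 0.

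Observed 77, expected 111.88, variance 16.88. Chi-square = (77 − 111.88)²/16.88 = 72.06 on 1 df, p = 2.1e-17. A two-sided p of 0.05 needs 3.84. The printed 0.05 is not reproduced.

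**4. Variations on the counts**

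- All 70 last-interval patients censored: chi-square unchanged at 72.06.
- Only the 13 last-interval silodosin patients censored: the last interval contributes E = 57×57/70 = 46.41 and V = 1.62. Expected is 101.29, variance 18.50, chi-square 31.89, p = 1.6e-8.
- Approximate bar-chart counts (5/20/57 and 55/30/13): chi-square 70.8.
- The Abstract's 89 and 93 patients, with the 12 extra tamsulosin patients assumed removed before day 14 and the 9 fewer silodosin patients taken from that same row (18/14/57 and 43/37/13): chi-square 44.3.
- Tamsulosin patients moved from the last row to the first: 33 moved gives p = 0.043, 34 moved gives p = 0.071. So 34 of the 57 would have to be in the wrong row.

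**5. Unknown days within intervals.** Whole days were drawn at random within 1–13, 14–21 and 22–28, 20,000 times per scheme.

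| Scheme | Largest p |
|---|---|
| Even spread | 1.6e-7 |
| Separate random daily profile per arm | 6.9e-6 |
| Even spread, the 13 silodosin patients censored at day 28 | 2.4e-4 |
| Separate profiles, the 13 censored at day 28 | 9.8e-4 |

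No draw reached 0.05. Deliberately adverse patterns do move the result:

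- No ties, every tamsulosin removal before every silodosin removal in each interval: chi-square 8.94, p = 0.0028.
- Worst whole-day pattern found by search, with all silodosin removals on the last day of each interval: chi-square 5.41, p = 0.020.
- Every tamsulosin removal at its own moment, with silodosin removals tied at each interval's end: expected 86.98, variance 31.21, chi-square 3.19, p = 0.074.

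The last pattern shows that p = 0.05 is not mathematically impossible. It is not a plausible set of clinical times.

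**6. The 0.001 beside these rows.** The document does not name the test. A Pearson chi-square on the 3×2 table gives 72.4 on 2 df (p about 2e-16), so it is most likely a table association test whose p is below 0.001. It is not evidence about the log-rank p.

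**The case against.** The strongest reply concedes the wording conflict and disputes the rest.

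- **The mismatch is conditional.** The sentence calls the result significant, so 0.05 is naturally read as the threshold or as p<0.05, and the numerical discrepancy then disappears. This stands, and the numerical part is put forward only on that condition. It does not rescue the text, because the other two readings are then wrong.
- **The times cannot be seen.** Individual days and the Figure 3 curve are not available, and the log-rank analysis set is not stated: the Abstract gives 180 patients but arms of 89 and 93, which sum to 182. This also stands. It limits the numerical part to implausibility, and the 89/93 variation above still gives chi-square 44.3.
- **The Conclusion does not cite the log-rank test.** The counts alone support its direction, the Figure 2 sentence is hedged, and the Abstract sentence reports counts. All of this is fair. Correcting the test would not reverse the direction. The unqualified statement about time is in the Conclusion, and that is where the caveat given under Figure 3 was lost.
- **Time to expulsion is not the defined outcome.** True, but the report presents it as a main finding.

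**Conclusion.** The concern holds, and the text is wrong as written. The three interpretations under Figure 3 cannot all be true under the report's own rule of p below 0.05, and this part rests on no assumption.

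If 0.05 is the computed log-rank p, it also does not plausibly fit the tabulated counts: chi-square is 72.1 on the grouped data, and 31.9 with the 13 last-interval silodosin patients censored, against 3.84. That part assumes a two-sided test and that the log-rank test used the same 179 patients as the table. It is a judgement of plausibility, not a bound.

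The direction of the counts is not in question. What is in question is the printed test result and what the report may say about it. This must be fixed.

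**What to change.** 1. State whether 0.05 is the test result, the threshold, or a misprint of p<0.05.
2. Re-run the log-rank test on the recorded expulsion days, censoring at 4 weeks any patient who had not expelled the stone. If only the three intervals were recorded, use a grouped or interval-censored test.
3. Report the statistic, degrees of freedom and exact p, with the number analysed, events and censored patients per arm.
4. Under Figure 3, keep one interpretation that follows from the p<0.05 rule and delete the statement that the times were comparable. Align the Figure 2 text, Abstract and Conclusion with it.
5. State that the log-rank test was not in the planned analysis. Add that a small p alone would not establish a drug effect, since the analysed arms are 77 and 102 and differ on laterality, symptom duration and stone position (each p printed as 0.001).

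The cost is one re-analysis and a few edited sentences, and slightly more if only interval categories exist. Even without re-analysis, the contradictory sentences must be reconciled.

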The side effects that patients using silodosin and tamsulosin experienced are analyzed in the table, and the p-value denotes the statistical significance of these data. Patients on Silodosin, with no side effects were 59.9% while 40.1% on Tamsulosin did not report any side effects. This implies that, in comparison to Tamsulosin, Silodosin may have a marginally higher correlation with patients reporting no adverse effects.

Examining particular side effects reveals various themes. Nine patients on tamsulosin (60.0%) and six patients on silodosin (40.0%) developed orthostatic hypotension, a condition marked by a considerable drop in blood pressure upon

standing. It suggested that Tamsulosin users are more likely to have orthostatic hypotension than Silodosin users.

Only a very tiny percentage of patients reported abnormal ejaculation; 2 individuals on tamsulosin (66.7%) and 1 patient on silodosin (33.3%). Again, this points to an increased chance of this specific adverse effect in Tamsulosin users.

[figure not shown]
Another side effect that was identified involved headaches, which were seen by 4 individuals on silodosin (44.4%) and 5 patients on tamsulosin (55.6%). Headaches were marginally more common among Tamsulosin users compared to Silodosin users, similar to orthostatic hypotension.

None of the detected differences in side effect distribution between Tamsulosin and Silodosin is statistically significant, according to the p-value of 0.315. This implies that even if there are discernible variations in the frequency of particular adverse effects between the two drugs, these variations might just be the result of random variation rather than an actual distinction in the side effect profiles of tamsulosin and silodosin.

In conclusion, the analysis of side effects reveals that patients taking silodosin have a tendency to report no side effects more often than individuals taking tamsulosin. On the other hand, it seems that tamsulosin users are more likely to experience certain adverse effects, like headache, orthostatic hypotension, and abnormal ejaculation. Even with these findings, the absence of statistical significance suggests that more investigation using larger sample sizes would be necessary to conclusively identify any significant variations in the side effect profiles of Tamsulosin and Silodosin.

Figure 2

Bar Chart showing comparison of stone expulsion rate in Tamsulosin and

Silodosin groups

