Only a very tiny percentage of patients reported experiencing abnormal ejaculation; 2 individuals on tamsulosin (66.7%) and 1 patient on silodosin (33.3%) reported this side event. Again, this points to an increased chance of this specific adverse effect in Tamsulosin users, but the numbers are too low to make any firm conclusions. Another side effect that was identified involved headaches, which were seen by 4 individuals on silodosin (44.4%) and 5 patients on tamsulosin (55.6%). Headaches were marginally more common among Tamsulosin users compared to Silodosin users, similar to orthostatic hypotension.

Many urologists agree when it comes to the incidence of retrograde ejaculation that it is an indication of therapy efficacy rather than a negative effect. It seems that silodosin relaxes the smooth muscles in the genital and lower urinary tracts sufficiently to cause a retrograde ejaculation. Retrograde ejaculation was more common in the individuals who experienced the most alleviation from lower urinary tract symptoms, which was consistent with this conclusion. This finding implies that the retrograde ejaculation is, in fact, a passive marker of the smooth muscle relaxation brought on by silodosin(32).

Typically, nonselective $\alpha 1$ adrenoceptor antagonists such doxazosin and terazosin are linked to orthostatic hypotension. Nonetheless, in clinical trials, silodosin was linked to a modest incidence of orthostatic hypotension. According to the combined analysis of the US and European studies, 1.1% of patients receiving a placebo and 1.3% of patients receiving silodosin experienced orthostatic hypotension(48).

When compared to Tamsulosin, Silodosin is linked to a larger incidence of retrograde ejaculation but a reduced incidence of peripheral vasodilation-related adverse effects, such as orthostatic hypotension and dizziness, according to a retrospective review conducted by Imperatore et al(49).

In our study comparing the effects of Tamsulosin and Silodosin on patients, it was discovered that only 38.1% of those receiving Silodosin needed analgesics to ameliorate ureteric pain. On the other hand, 61.9% of patients receiving Tamsulosin required analgesic intervention, which is a far larger percentage. This significant difference raises the possibility that silodosin is more successful in treating ureteric stones and it also lowers their need for extra painkillers.

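### The abstract and Conclusion claim a safety advantage for silodosin that the trial's own side-effect comparison does not show, and the supporting percentages are shares of cases, not rates within arms

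*Combined protocol and SAP*

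**What the plan says.** The Objectives include a comparison of side-effect profiles. The Alternative Hypothesis is that silodosin is better in both efficacy and safety. The Data Analysis Procedure sets significance at p below 0.05, names only a t-test, and does not say whether tests are one- or two-sided.

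In Results, the text on the side-effect table gives p = 0.315 and says "None of the detected differences in side effect distribution between Tamsulosin and Silodosin is statistically significant". It adds that the differences may be random variation and that "the absence of statistical significance suggests that more investigation using larger sample sizes would be necessary". On abnormal ejaculation, the Discussion says there is a higher chance on tamsulosin, "but the numbers are too low to make any firm conclusions".

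The summary statements read differently. The abstract says silodosin was "better in expulsing stone as well as in producing lesser side effects and hence better safety profile than Tamsulosin". The Conclusion says "According to our findings, silodosin has a safer profile and is more successful than tamsulosin at ejecting ureteric stones", and that "patients treated with silodosin reported fewer side effects, such as a retrograde ejaculation, orthostatic hypotension and headaches as compared to those taking Tamsulosin". Neither place carries the caveat from Results.

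The percentages take this form: in the abstract, "Nine patients on tamsulosin (60.0%) and six patients on silodosin (40.0%) developed orthostatic hypotension"; in Results, "Patients on Silodosin, with no side effects were 59.9% while 40.1% on Tamsulosin did not report any side effects".

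**The concern.** Safety is half of the alternative hypothesis. Results treats the safety comparison as inconclusive, but the abstract and Conclusion, which most clinicians will act on, treat it as settled in favour of silodosin. The Conclusion attributes the claim to this trial's findings, so it cannot be read as a summary of the literature.

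The percentages add to the problem. A reader of the abstract, who has no table, could take 60.0% as the risk of orthostatic hypotension on tamsulosin. The figures for patients without side effects are worded as though they were rates on each drug.

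**Working it through.** **Inputs** (side-effect table in Results; tamsulosin, silodosin): none 61, 91; orthostatic hypotension 9, 6; abnormal ejaculation 2, 1; headache 5, 4. The columns sum to 61 + 9 + 2 + 5 = 77 and 91 + 6 + 1 + 4 = 102. The total is 179, which matches the Results text.

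**1. The reported p-value.** Pearson chi-square is the sum of (observed - expected)²/expected, with expected = row total × column total / 179. The row contributions are:
- none: 0.516
- orthostatic hypotension: 1.765
- abnormal ejaculation: 0.685
- headache: 0.577

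The sum is 3.543 on 3 df, p = 0.315, so the printed figure reproduces. An exact test on the same table gives p = 0.322, so small expected counts do not change the reading.

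**2. Any tabulated reaction.** The 3-df test spreads the evidence over four categories, so the collapsed comparison is the fairer test of overall safety.
- Tamsulosin: 9 + 2 + 5 = 16; 16/77 = 20.8%.
- Silodosin: 6 + 1 + 4 = 11; 11/102 = 10.8%.
- Difference: 0.2078 - 0.1078 = 0.0999, or 10.0 points.
- SE = √(0.2078 × 0.7922/77 + 0.1078 × 0.8922/102) = 0.0555.
- 95% CI: 10.0 ± 1.96 × 5.55 = -0.9 to 20.9 points (Newcombe -0.7 to 21.3).
- Risk ratio, silodosin to tamsulosin: 0.52 (0.26 to 1.05).
- Two-sided p: Pearson 0.064, Fisher 0.090, Yates 0.101. The plan's t-test applied to the 0/1 indicator gives 0.065.

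None of these is below 0.05.

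**3. Printed shares against rates within arms.**

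| Row | Printed (tamsulosin, silodosin) | Within arm |
|---|---|---|
| No side effects | 40.1%, 59.9% | 61/77 = 79.2%, 91/102 = 89.2% |
| Orthostatic hypotension | 60.0%, 40.0% | 9/77 = 11.7%, 6/102 = 5.9% |
| Headache | 55.6%, 44.4% | 5/77 = 6.5%, 4/102 = 3.9% |

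Within arms, orthostatic hypotension differs by 5.8 points (Newcombe -2.5 to 15.4; Fisher p = 0.18) and headache by 2.6 points (-4.2 to 10.8; p = 0.50).

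Silodosin patients are 102/179 = 57.0% of those analysed, so about 57% of unaffected patients would be on silodosin even with no drug difference. The printed gap for no side effects is 59.9 - 40.1 = 19.8 points; the gap within arms is 89.2 - 79.2 = 10.0 points.

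For the named reactions the distortion runs the other way, because the ratio of shares equals the risk ratio times 77/102 = 0.755:
- orthostatic hypotension: 60.0/40.0 = 1.5 against a risk ratio of 1.99
- headache: 5/4 = 1.25 against 1.66
- abnormal ejaculation: 2/1 = 2.0 against 2.65 on all-patient denominators

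The last of these needs a men-only denominator, since 74 of the 179 patients are women. Men per arm are not reported.

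**The case against.** **The Results section is candid.** It prints the p-value, allows for chance and asks for larger samples, and the Discussion is cautious on ejaculation. This stands, so it would be wrong to infer that the non-significance was concealed. The fault is limited to the abstract and Conclusion.

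**Fewer side effects is literally true.** The silodosin count is lower in every reaction row and overall (11 against 16). As description it can stay. The step from fewer reports to a safer drug is what lacks support.

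**The figure 0.315 understates the evidence.** A reader might attach it to 16/77 against 11/102. It belongs to the four-category table. The collapsed comparison gives 0.064 to 0.101, which is closer to the threshold but still above it.

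**The alternative is directional.** One-sided, the collapsed comparison would give 0.032 (Pearson) or 0.051 (Fisher), so the result would depend on the test chosen. But the plan declares no one-sided test, and its sample size fits a two-sided one: 64% against 83% at 80% power needs 94 per arm with continuity correction, and 94 × 1.1 = 103.4, which rounds up to the planned 104.

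**Case shares flatter silodosin throughout.** A reader might infer this, but it holds only for the no-side-effect row. For each named reaction the shares understate the relative difference (for ejaculation, on all-patient denominators).

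**Conclusion.** The concern holds for the two safety claims and for the percentages. At 0.05, two-sided (an assumption, since the plan is silent), a safety advantage for silodosin was not shown: p = 0.315 over four categories, and 0.064 to 0.101 for any tabulated reaction.

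The opposite inference, that the two drugs are equally safe, is not supported either. The point estimate favours silodosin by 10.0 points, and the interval runs from 0.9 points in favour of tamsulosin to 20.9 in favour of silodosin. An advantage is neither shown nor excluded.

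The interval itself should not be read as a clean randomised estimate. The tables analyse 77 and 102 patients out of a planned 104 and 104, and they report p = 0.001 for imbalances in laterality, time from symptoms to CT, and stone position. The abstract gives 89 and 93, which sum to 182, not its stated 180. Those arm sizes cannot describe a side-effect table that lists 102 silodosin patients, so all figures here use 77 and 102.

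**What to change.** 1. **Reconcile the arm sizes first:** 77 and 102 in the tables against 89 and 93 in the abstract, and 182 against 180.
2. **Withdraw the safety claims** from the abstract and Conclusion. If 77 and 102 are confirmed, say instead that tabulated reactions were numerically fewer on silodosin (11/102, 10.8%) than on tamsulosin (16/77, 20.8%), difference 10.0 points, 95% CI -0.9 to 20.9, not statistically significant, and that the safety part of the alternative hypothesis was not shown. The Conclusion's sentence on fewer side effects may stay if labelled numerical and not significant.
3. **Replace shares of cases** in the abstract, the side-effect results and the matching Discussion text with n/N by arm, a risk difference and a 95% CI. Use men only for abnormal ejaculation, with men per arm taken from the dataset.
4. **Add a caveat** beside the estimate on the uneven analysed arms and the baseline imbalances.

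The cost is wording, percentages recalculated from counts already printed, and one tabulation of sex by arm. No new data collection is needed. The trial gives up a favourable safety statement that its own analysis does not support.
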